In this substudy, a select number of subjects at selected sites in English-speaking countries who are enrolled in CNTO136ARA3004 will be consented and enrolled in a SmartJect™ AI Usability substudy. Site personnel in this substudy will observe and document 2 scheduled self-administrations of study agent by subjects using the PFS-AI. All substudy subjects will also complete an e-diary regarding their experiences with at-home use of PFS-AI.

STATISTICAL METHODS

Statistical analysis will be done by the Sponsor or under the authority of the Sponsor.

Subjects will continue to receive the same treatment regimen administered in studies CNTO136ARA3002 and CNTO136ARA3003 at Weeks 104 and 52, respectively:

- Group 1: Sirukumab 100 mg SC q2 weeks
- Group 2: Sirukumab 50 mg SC q4 weeks

After the study becomes open-label, subjects in Group 1 will be offered the option (at the discretion of the investigator) to reduce the sirukumab dose to 50 mg q4 weeks for the remainder of the trial.

Since the treatment groups are not randomly assigned in this study, no formal hypothesis testing is planned. The efficacy, safety, and PK/PD/immunogenicity analyses will be performed separately for subjects who complete studies CNTO136ARA3002 and CNTO136ARA3003. The analyses will include all subjects enrolled by study and by treatment group above.

Only 1 DBL (at the end of the study) is planned. Safety, efficacy, and PK/PD/immunogenicity assessments will be analyzed for subjects enrolled in the CNTO136ARA3004 by previous study and by treatment group.

CNTO 136 (sirukumab): Clinical Protocol CNTO136ARA3004 – Amendment 3

Additional data releases or locks may occur as needed. The analyses based on these data releases or locks intend to integrate data from CNTO136ARA3002 and CNTO136ARA3003 with this study for the long-term PK, immunogenicity, safety and efficacy data of all subjects enrolled in these studies. A separate SAP for integration will be developed to specify the analyses and data handling rules.

- **Sample Size Determination**

All eligible subjects will be included in this LTE study. No power calculations were performed as there is no statistical hypothesis testing planned.

- **Interim Analysis**

No formal interim analyses are planned, though analyses based on interim releases and locks may be carried out for integrated PK, immunogenicity, safety and efficacy data.

- **Primary Analyses**

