The number of subjects with each of the following long-term safety events: cardiovascular SAEs, malignancies, serious infections, and gastrointestinal perforations will be summarized. Serious cardiovascular events adjudicated by the CEC will be summarized by treatment group. No hypothesis testing will be performed.

- **Secondary Analyses**

The laboratory parameters of interest (neutrophils, platelets, hepatobiliary parameters, and lipid parameters) will be summarized by the treatment group over time. Baseline value is defined as the baseline value of study CNTO136ARA3002 or CNTO136ARA3003, respectively.

- **Other Planned Analyses**

- **Safety Analyses**

Additional analyses will be performed for the number of patients with cardiovascular SAEs by cardiovascular type and the number of patients with malignancies by malignancy type (eg, lymphoma, nonmelanoma skin cancers, other malignancies).

Other safety data will be assessed by summarizing the proportion of subjects with AEs, the types of AEs, infections, SAEs, AEs leading to discontinuation, and changes in laboratory parameters.

- **Efficacy Analysis**

The following efficacy endpoints will be summarized by treatment group over time:

- ACR responses
- DAS28
- HAQ-DI
- SF-36

Baseline value in efficacy is defined as the baseline value of study CNTO136ARA3002 or CNTO136ARA3003. No missing data imputation will be used.

- **Medical Resource Usage and Health Economics**

WLQ and HECONQ data will be summarized over time.

- **Pharmacokinetic and Immunogenicity Analyses**

CNTO 136 (sirukumab): Clinical Protocol CNTO136ARA3004 – Amendment 3

Serum sirukumab concentration data including C_{trough} will be summarized. PK data may be displayed graphically. If sufficient samples are collected, steady-state trough serum sirukumab concentrations before and after switching from PFS-U to PFS-AI will be evaluated.

The incidence of antibodies to sirukumab will be summarized for subjects with appropriate samples for detection of antibodies to sirukumab (ie, at least 1 sample obtained after sirukumab administration).

- **Pharmacodynamic Analyses**

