11 STATISTICAL METHODS

Statistical analysis will be done by the Sponsor or under the authority of the Sponsor. Descriptive statistics (eg, mean, median, standard deviation, interquartile range, minimum, and maximum) will be used to summarize continuous variables. Counts and percentages will be used to summarize categorical variables.

Subjects will continue to receive the same treatment regimen administered in studies CNTO136ARA3002 and CNTO136ARA3003 at Weeks 104 and 52, respectively:

- Group 1: Sirukumab 100 mg SC q2 weeks
- Group 2: Sirukumab 50 mg SC q4 weeks

CNTO 136 (sirukumab): Clinical Protocol CNTO136ARA3004 – Amendment 3

After the study becomes open-label, subjects treated with SC sirukumab 100 mg q2 weeks will be offered the option to reduce the sirukumab dose to 50 mg q4 weeks at the investigator's discretion. This decision can be made at the subject's first or second major resupply visit (up until approximately 7 months) after implementation of Amendment 3 at the study site.

Since the treatment groups are not randomly assigned in this study, no formal hypothesis testing is planned. The efficacy, safety, and PK/PD/immunogenicity analyses will be performed separately for subjects who complete studies CNTO136ARA3002 and CNTO136ARA3003. The analyses will include all subjects enrolled by study and by treatment group above.

Additional data releases or locks may occur periodically as needed. The analyses based on these data releases or locks intend to integrate data from CNTO136ARA3002 and CNTO136ARA3003 with this study for the long-term PK, immunogenicity, safety and efficacy data of all subjects enrolled in these studies. A separate SAP for integration will be developed to specify the analyses and data handling rules.

An independent DMC will monitor the safety of the blinded portion of the study in unblinded fashion on a regular basis and whenever deemed necessary. Additional details are provided in Section 11.10.

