11.9 Interim Analysis

No formal interim analyses are planned, though analyses based on interim releases and locks may be carried out for integrated PK, immunogenicity, safety and efficacy data.

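### The protocol does not commit the final analysis of the primary safety events to a combined sirukumab summary or to any interval, so rare events would be shown only imprecisely, by parent study and dose

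*Protocol*

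**What the plan says.** The Synopsis (Statistical Methods) and Section 11 both state the split: "The efficacy, safety, and PK/PD/immunogenicity analyses will be performed separately for subjects who complete studies CNTO136ARA3002 and CNTO136ARA3003". For the single planned lock at the end of the study, the Synopsis adds that "assessments will be analyzed for subjects enrolled in the CNTO136ARA3004 by previous study and by treatment group". Section 11.1 bases analyses in general on the treatment groups of Section 11. Two parent studies and two dose groups make four cells.

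On the primary events, the Synopsis (Primary Analyses) says: "The number of subjects with each of the following long-term safety events: cardiovascular SAEs, malignancies, serious infections, and gastrointestinal perforations will be summarized". Section 11.2.1 says the same and names treatment group only for the adjudicated cardiovascular events. The summary statistic comes from Section 11: "Counts and percentages will be used to summarize categorical variables". No interval and no rate per unit of follow-up time is mentioned for these events.

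A combined analysis does appear, but on another footing. Section 11 says "Additional data releases or locks may occur periodically as needed" and continues: "The analyses based on these data releases or locks intend to integrate data from CNTO136ARA3002 and CNTO136ARA3003 with this study". The rules are deferred: "A separate SAP for integration will be developed to specify the analyses and data handling rules". Section 11.9 keeps it optional: "No formal interim analyses are planned, though analyses based on interim releases and locks may be carried out for integrated PK, immunogenicity, safety and efficacy".

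**The concern.** The primary objective is long-term safety, and every subject in this extension receives sirukumab. Section 1.1 and Section 3.2.6 single out GI perforation as an event reported with another agent of this kind, and such events are rare. When a rare event is spread over four cells, most cells will hold zero or one case. Each cell is then compatible with a wide range of rates, and a percentage without an interval does not show how wide.

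A reader who adds the four counts by hand obtains a total but no prespecified interval. Nor does that total allow for follow-up, which differs by parent study: up to 156 weeks for subjects from CNTO136ARA3002 and up to 208 weeks for those from CNTO136ARA3003 (Section 3.2.3). At stake is how precisely the final report can state its main safety result.

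**Working it through.** The protocol gives no sample size, cell size, event rate or precision target, so it has no figure to reproduce. Subject-years (SY) per cell and the true rate used below are assumptions.

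**Formulas.** For k events in T subject-years, the exact Poisson 95% limits are

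- lower = χ²(0.025; 2k) / (2T), taken as 0 when k = 0
- upper = χ²(0.975; 2k + 2) / (2T)

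For k = 0 the upper limit is 7.378 ÷ (2T) = 3.689 ÷ T.

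**Zero events, four equal cells.** One cell has T and the combined column has 4T.

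| SY per cell (assumed) | One cell, upper limit per 100 SY | Combined, upper limit per 100 SY |
|---|---|---|
| 300 | 3.689 ÷ 300 = 1.23 | 3.689 ÷ 1200 = 0.31 |
| 500 | 3.689 ÷ 500 = 0.74 | 3.689 ÷ 2000 = 0.18 |
| 1000 | 3.689 ÷ 1000 = 0.37 | 3.689 ÷ 4000 = 0.09 |

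The ratio is 4 in each row, as it must be with equal cells.

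**One event per cell, 500 SY per cell.** One cell (k = 1, T = 500) gives 0.005 to 1.11 per 100 SY. Combined (k = 4, T = 2000) gives 0.05 to 0.51.

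**How often a cell is empty.** At an assumed true rate of 0.2 per 100 SY and 500 SY per cell, 0.002 × 500 = 1 event is expected per cell. P(no event in a given cell) = exp(−1) = 0.37. P(all four cells show at least one event) = (1 − 0.368)⁴ = 0.16.

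**Unequal cells.** With zero events, the ratio of a cell's upper limit to the combined one is 1 divided by that cell's share of the subject-years. Take an assumed 2000 SY in total, with cells holding 37.5%, 37.5%, 12.5% and 12.5%:

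- large cell: 3.689 ÷ 750 = 0.49 per 100 SY, ratio 1 ÷ 0.375 = 2.7
- small cell: 3.689 ÷ 250 = 1.48 per 100 SY, ratio 1 ÷ 0.125 = 8
- combined: 0.18 per 100 SY, unchanged

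**Check on the proportion scale.** The exact binomial 95% upper limit for 0 of 500 subjects is 0.735%, and for 0 of 2000 it is 0.184%. The ratio is again about 4.

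**Follow-up.** 156 ÷ 52 = 3 years and 208 ÷ 52 = 4 years at most. A pooled percentage would therefore mix different lengths of observation, so the combined summary needs person-time denominators.

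**The case against.** There is a fair case for the separate presentation. The two parent studies enrolled different populations, their follow-up in the extension differs, and the groups are not randomised here. Section 1.2 reports more hypersensitivity and injection-site reactions at 100 mg q2 weeks than at 50 mg q4 weeks, so a table that only pooled doses could hide dose-related harm. The study tests no hypothesis and sets no decision threshold. SAE reports go to the DMC on an ongoing basis (Section 11.10), so individual rare cases are not overlooked. All of this supports keeping the separate columns; none of it argues against a descriptive total beside them.

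The integration analysis is the stronger reply, because it would add parent-study exposure and so pool more data than a combined column here. It is, however, optional and tied to releases made as needed, and its rules lie in another plan. It also covers a different span from this study's primary endpoint. It reduces the concern without removing it.

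A reader might infer more than the documents support:

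- **That no combined estimate is foreseen anywhere.** Integration is foreseen. What is missing from the protocol is a commitment in this study's final analysis.
- **That only raw counts are given.** Section 11 adds percentages.
- **That each event is judged on a quarter of the data.** No cell sizes are given, all four cells are reported, and no rule rests a judgement on one cell.
- **That lymphoma is a primary event.** The primary event is malignancies. Lymphoma is a subtype in the additional analyses of Section 11.8.
- **That the SAP also lacks a total column and intervals.** Its text was not available, so this cannot be said.

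**Conclusion.** The point holds for the protocol text. The final analysis of the four primary event types is specified by parent study and dose group as counts and percentages, with no committed combined summary and no interval. For rare events this costs precision. With four equal cells and no events, the exact 95% upper limit in one cell is about four times the combined limit: 0.74 against 0.18 per 100 SY at an assumed 500 SY per cell. That multiple follows from assuming equal cells. With unequal cells it is smaller in the large cells and larger in the small ones.

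A further reason favours a combined column. Group 1 subjects may reduce their dose in the open-label phase, and the protocol gives no explicit rule for which dose column counts a later event. The all-sirukumab column is unaffected by that choice.

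This is a worthwhile improvement to the primary table. It does not invalidate the study, and no data are lost under the present plan.

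**What to change.** In Section 11.2.1 and the matching Synopsis text, keep the parent-study-by-dose columns and add:

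1. an all-sirukumab column covering both parent studies and both doses;
2. for each primary event in every column: the number of subjects with the event, the subject-years at risk, the incidence per 100 subject-years, and an exact Poisson 95% confidence interval. State when time at risk starts and stops.

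Label the intervals descriptive and state that no hypothesis test is attached. No stratified interval is needed, since the retained columns show any difference by parent study or dose. If the SAP already contains these elements, align the protocol text with it.

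The cost is a somewhat larger table and a written definition of time at risk. No new data and no change in conduct are needed. The combined column does mix two populations and two doses, so it should be read beside the separate columns and not in their place.

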1 INTRODUCTION

CNTO 136 (sirukumab) is a human anti-IL-6 mAb currently under development by the Sponsor in collaboration with GlaxoSmithKline, plc. It binds to human IL-6 with high affinity and specificity, and has been shown to inhibit IL-6-mediated signal transducer and activator of transcription-3 (STAT3) phosphorylation, resulting in the inhibition of the biological effect of IL-6. The target indications for sirukumab are rheumatoid arthritis (RA) and lupus nephritis (LN), both of which are diseases that involve IL-6.

IL-6 is a pleiotropic cytokine known for proinflammatory functions.¹⁹ The physiological and pathological role of IL-6 has been illustrated in many in vitro and in vivo studies which collectively suggest that IL-6 induces the differentiation of B cells into antibody-producing cells; promotes the development of cytotoxic T cells³⁴; supports differentiation of Th17 cells; affects macrophage differentiation³²; is an independent regulator of granulopoiesis²⁴; increases hepatic acute-phase reactants, and promotes mesangial cell proliferation, keratinocyte growth, megakaryocytic differentiation, and thrombosis.¹⁶ IL-6 levels are increased in obesity, as IL-6 is produced from adipose tissue.⁴⁶ Increased levels of IL-6 also correlate with insulin resistance.³⁷ IL-6 blockade has been shown to have a potent effect on neutrophil recruitment.³⁰

IL-6 knockout mice have a normal phenotype. The animals are viable and fertile, but have a slightly decreased number of T-cells and a decreased acute phase protein response to tissue injury.²⁰ IL-6 deficient mice have been noted to be susceptible to infections with *Listeria monocytogenes*, *Toxoplasma gondii*, and *Candida albicans*.^{6,38,44} In contrast, transgenic mice that over-express IL-6 in lymphoid cells have massive plasmacytosis, increased megakaryocytes, and mesangial cell proliferation in the kidney.⁴³ Over-expression of IL-6 in the brain results in neurologic disease such as neurodegeneration, astrocytosis, and proliferative angiopathy.⁵

Published studies have demonstrated the involvement of IL-6 in various disease processes including lupus erythematosus (LE), RA, anemia of chronic inflammation, insulin resistance, and cancer.

1.1 IL-6 as a Target in Rheumatoid Arthritis

Patients with RA often have increased levels of proinflammatory cytokines such as IL-6, IL-1, and tumor necrosis factor alpha (TNF α)³ in the synovial fluid and serum. TNF α and IL-1 both can stimulate IL-6 production by multiple cell types in the RA synovium.¹³ Local concentrations of IL-6 may in turn stimulate leukocyte recruitment to the joint, promote osteoclast maturation and activation, suppress chondrocytes, and stimulate synovial proliferation, contributing to joint damage.^{11,23} Systemically, elevated IL-6 in patients with RA may induce hepatic production of acute phase proteins, increase platelet production, and the development of anemia of chronic inflammation via induction of hepcidin.³¹ It also may be chiefly responsible for autoimmune features in RA such as autoreactive T cell activation and hypergammaglobulinemia.¹⁷

Early studies focused on IL-6 signaling identified 2 mechanisms for signal transduction. The first occurs when IL-6 binds specifically to the membrane-bound IL-6 receptor (IL-6R, or CD126). This IL-6/IL-6R complex then binds 2 gp130 co-receptor molecules (CD130) on the cell membrane and triggers gp130-dependent intracellular signaling cascades via the janus

CNTO 136 (sirukumab): Clinical Protocol CNTO136ARA3004 – Amendment 3

kinase/signal transducer and activator of transcription (JAK/STAT) and rat sarcoma viral oncogene homolog (RAS) pathways. While gp130 is expressed on many cell types, the expression of membrane IL-6R is restricted to hepatocytes, neutrophils, monocytes, and other leukocyte populations and hence this classical or “cis” signaling mechanism is limited to these cell types. However, a second mechanism was discovered when it was reported that soluble IL-6R (sIL-6R) can be secreted as a truncated form of the IL-6R in cells, or released from the cell surface due to proteolytic cleavage of membrane-bound IL-6R.^{25,29} IL-6 can form complexes with sIL-6R, and then initiate signaling on cells that express only the gp130 co-receptor.²⁶ This “trans” signaling therefore extends the effects of IL-6 to many other cell types that do not express endogenous IL-6R.³⁹

Sirukumab binds to IL-6 and prevents its binding to both the membrane and soluble forms of IL-6R and therefore will provide similar inhibition of both “cis” and “trans” signaling due to IL-6. In contrast, tocilizumab binds to the membrane and soluble forms of IL-6R in order to prevent IL-6 signaling.²⁸ Tocilizumab inhibits signal transduction mediated by both mIL-6R and sIL-6R, but not by the receptors of other members of IL-6 cytokine family.²⁸ As a result, tocilizumab may not be as potent for the neutralization of “cis” signaling due to lower affinity for membrane IL-6R, or the cells expressing membrane IL-6R may be less accessible. In addition, tocilizumab is a human IgG1 antibody that, when bound to membrane IL-6R, potentially can trigger cell lysis via complement or fragment crystallizable (Fc) receptor-expressing natural killer (NK) cells.^{4,14,40}

IL-6 inhibition results in improvement in patients with active arthritis.^{21,33,51} The effectiveness of the anti-IL-6 receptor mAb, tocilizumab, in reducing joint swelling and tenderness, improving physical function, and reducing the rate of radiographic progression was firmly established in pivotal registration studies.^{7,18,21,33,41} Additionally, in smaller RA studies biologic agents targeting the IL-6 cytokine ligand have also been shown to be efficacious.^{27,49}

Safety issues related to the inhibition of IL-6 inhibition by tocilizumab include increased risk of serious infections and abnormalities in hematology, hepatobiliary, and lipid parameters. In addition, upper and lower gastrointestinal tract perforations occurred in the anti-IL-6 receptor (tocilizumab) Phase 3 program. The potential differences in safety or efficacy between agents that bind to the IL-6 receptor versus ones that bind to the IL-6 ligand (sirukumab) remain unclear, but warrant further study.

In summary, IL-6 plays a major role in the pathophysiology of RA, and this is confirmed by the efficacy of IL-6 and IL-6 receptor inhibitors in clinical studies of patients with inflammatory arthritis.

For the most comprehensive nonclinical and clinical information regarding the efficacy and safety of sirukumab, refer to the latest version of the Investigator's Brochure for sirukumab.

The term "Sponsor" used throughout this document refers to the entities listed in the Contact Information page(s), which will be provided as a separate document.

1.2 Overall Rationale for the Study

This is a parallel-group long-term extension (LTE) trial of studies CNTO136ARA3002 and CNTO136ARA3003 to assess the long-term safety and efficacy of sirukumab in subjects with moderately to severely active RA. Subjects who have completed participation in studies CNTO136ARA3002 or CNTO136ARA3003 will be eligible to enroll in this study. Subjects are to continue to receive the identical sirukumab SC dose regimen of 100 mg every 2 (q2) weeks or 50 mg every 4 (q4) weeks that they were receiving upon completion of participation in studies CNTO136ARA3002 and CNTO136ARA3003.

Following the database lock for the primary endpoint, analysis of CNTO136ARA3002 and CNTO136ARA3003 PK and efficacy data showed that there was no clear dose response between the sirukumab SC 50 mg q4 weeks and sirukumab SC 100 mg q2 weeks dose groups across efficacy endpoints. Furthermore, there were a greater proportion of subjects with hypersensitivity reactions and injection site reactions in the sirukumab 100 mg q2 weeks dose group compared with the sirukumab 50 mg q4 weeks dose group. Therefore, to allow for minimization of the exposure to this immunosuppressant biologic agent, subjects treated with SC sirukumab 100 mg q2 weeks will be offered the option to reduce the sirukumab dose to 50 mg q4 weeks at the investigator's discretion after the study becomes open-label. This decision can be made at the subject's first or second major resupply visit (up until approximately 7 months) after implementation of Amendment 3 at the study site. Once a subject's dose is reduced to 50 mg q4 weeks, the subject will receive that dose for the remainder of the trial (ie, a return to 100 mg q2 weeks will not be allowed). If a subject opts to remain on the sirukumab 100 mg q2 weeks dose, he or she will remain on that dose for the duration of their participation in the study (ie, the subject will not have the option to reduce the dose at a subsequent timepoint).

Additionally, a substudy of enrolled subjects in CNTO136ARA3004 will further assess the usability of the SmartJect™ Autoinjector (PFS-AI).

